10.3 Accrual

A total of 40 evaluable patients will be enrolled across three investigational sites. The estimated enrollment rate across the three sites is 3 patients per month, leading to anticipated enrollment duration of approximately 14 months. The duration from first patient enrolled to primary analysis is approximately 18 months, and the total study duration including follow upis expected to be 3 years.

10.4 Interim Analysis

There will be an interim analysis for safetyafter 10 patients have received a minimum of 8 weeks of protocol therapy. Study accrual will continue during the interim safety analysis.

If, after 8 weeks of protocol therapy, four or more out of ten patients have a grade 3 or higher adverse event that the study investigator deems as possibly, probably, or definitely related to study drug (excluding hypokalemia or hypertension), the study will close to further accrual.

An interim analysis for lack of efficacy will be performed after completion of the first stage of accrual of 22 patients. Study accrual will not stop for this analysis, consistent with the study design of prior non-hormonal therapies in biochemically relapsed prostate cancer, the majority of which were single stage phase II studies without pre-specified stopping rules for lack of efficacy despite observed PSA response proportions of less than 5%.

10.5 Analysis Population

The primary efficacy analysis will include all patients who have at least one PSA follow-up measurement. In addition, if a patient comes off study prior to obtaining one PSA follow-up measurement for disease progression or toxicity, they will be included in the analysis of PSA response as a treatment failure. All patients who receive at least one dose of study drug will be included in the analysis of safety.

10.6 Demographics and Baseline Characteristics

Demographic variables will include age, race, ethnicity, height, and weight. Baseline characteristics will include the following:

- Number of years since diagnosis of prostate cancer
- Gleason grade/clinical stage/pathologic stage (if prior prostatectomy)/PSA at the time of diagnosis
- Type and timing of local therapy (surgery and/or radiation) for prostate cancer
- Nadir PSA after definitive local therapy and time to nadir PSA
- Time from definitive local therapy to PSA progression (as defined by first $PSA \ge 0.2$ ng/mL in patients with prior radical prostatectomy with or without adjuvant radiation therapy; first PSA rise of 2.0 ng/mL or more above the nadir in patients with prior primary definitive radiation therapy)
- Time interval from biochemical relapse to study entry
- PSA doubling timeat the time of study entry
- Use of prior ADT, nadir PSA on ADT, duration of ADT, time interval from last dose of ADT and study enrollment, and indication (i.e. adjuvant or in biochemical relapse) (if applicable)
- Use of prior antiandrogen therapy, time interval since prior therapy to study enrollment, and indication (if applicable)

10.7 Study Endpoints

10.7.1 Primary Endpoint

The proportion of patients with biochemically relapsed disease after prior definitive local therapy who achieve $a \ge 50\%$ decline from baseline in serum PSA after 12 weeks of therapy with itraconazole, confirmed by repeat measurement at least 2 weeks later, will be calculated.

10.7.2 Secondary Endpoints

A) Clinical Activity:

- Median time to PSA progression among men with biochemical relapse treated with itraconazole will be estimated. See Section 2 for the definition of PSA progression.
- Median time to clinical progression will be estimated, with clinical progression defined as the first occurrence of either development of overt metastases or initiation of non-protocol therapy. The definition of clinical progression excludes PSA-only progression.
- Median metastasis-free survival will be estimated among men with biochemical relapse treated with itraconazole.
- Mean percent change after 12 weeks of protocol therapy compared with pre-treatment in PSA doubling time will be determined for those treated with itraconazole. The pre-treatment PSADT will be determined based upon all PSA measurements within 3 months prior to Day 1 of protocol therapy, with a minimum of three PSA values each spaced at least 14 days apart (see Section 6.2.1).

B) Safety/Pharmacokinetics:

- Maximum grade toxicities observed during treatment with itraconazole, as graded by CTCAE version 4.03.
- Mean steady-state trough level of serum itraconazole and its active metabolite, hydroxyitraconazole, after 4 weeks of therapy with itraconazole.

10.7.3Correlative Endpoints

A) Endocrine Parameters:

- Mean percent change from baseline in serum androgen levels, including serum testosterone, DHEA-S, and androstenedione, after 4 and 12 weeks of protocol therapy.
- Mean percent change from baseline in additional serum hormone levels, including ACTH, aldosterone, deoxycorticosterone (DOC), 11-deoxycortisol, and cortisol after 4 and 12 weeks of protocol therapy.
- Mean baseline and mean percent change in serum hormone levels among patients achieving $\geq 50\%$ decline from baseline in serum PSA after 12 weeks of itraconazole therapy and among those not achieving this decline.

B) Hedgehog Pathway (assessed by serial skin biopsies on protocol therapy and analysis of archived primary prostate cancer tissue including prior biopsy or prostatectomy specimen):

- Proportion of patients who display a down-regulation of the Hedgehog pathway, as assessed by measurement of *GLI1* mRNA expression by RT-PCR on serial skin biopsies obtained at baseline and after 4 weeks of protocol therapy with itraconazole. Down-regulation will be defined as a decline of any magnitude in GLI1 mRNA expression after 4 weeks of protocol therapy compared to baseline expression level.
- Proportion of patients with and without at least a 50% decline from baseline after 12 weeks of protocol therapy in PSA exhibiting a down-regulation of the Hedgehog pathway.
- Median time to PSA progression between patients with and without down-regulation of the Hedgehog pathway on itraconazole therapy as assessed by serial skin biopsy.
- Proportion of patients with and without at least 50% decline from baseline after 12 weeks of protocol therapy in PSA exhibiting over-activation of Hedgehog pathway components as assessed by immunohistochemical (IHC) and mRNA expression analysis of primary prostate cancer tissue (prior biopsy or prostatectomy specimen). Patients will be dichotomized (immunohistochemical staining 0 to 1+ vs. 2 to 3+ staining intensity; mRNA expression above and below median) for the purposes of analysis of the Hedgehog pathway in primary prostate cancer tissue.
- Median time to PSA progression between patients with and without Hedgehog pathway over-activation in archived primary prostate cancer tissue.

10.8 Methods for Analysis

10.8.1 Analytic Plan for the Primary Objective

The primary objective will be evaluated following the decision rules for Simon''s minimax 2 stage design as defined above (Section 10.2). The proportion of patients who achieve $a \ge 50\%$ decline in serum PSA compared to baseline after 12 weeks of protocol therapy, confirmed by repeat measurement at least two weeks later, will be calculated.Patients with at least one PSA follow-up measurement who discontinue protocol therapy prior to 12 weeks due to any reason will be counted as failures for analysis of the primary objective. In addition, patients who discontinue protocol therapy due to disease progression or toxicity prior to obtaining one PSA follow-up measurement will be counted as failures for analysis of the primary objective. Patients who withdraw from the study for other reasons prior to one PSA follow-up measurement will be excluded in the analysis of the primary objective. The null hypothesis is that 10% of patients will achieve $a \ge 50\%$ decline in serum PSA after 12 weeks of protocol therapy, with an alternative hypothesis that 25% of patients will achieve such a decline in serum PSA. If accrual is completed and at least 8 patients achieve $a \ge 50\%$ decline in serum PSA from their baseline measurement then the null hypothesis will be rejected based upon a test with 80% power and a

directional level of significance of 5%. The results will be summarized by the proportion of patients who achieve $a \ge 50\%$ decline in serum PSA along with a 95% confidence interval.

The mean percent changein PSA doubling time after 12 weeks of protocol therapy from pretreatment PSA doubling timewill be calculated. Calculation of baseline PSA doubling time will be based upon all PSA measurements obtained within 3 months prior to Day 1 of protocol therapy, with a minimum of threePSA values spaced at least 14 days apart(see Section6). The PSA doubling time both pre- and on-treatment will be estimated using the relationship of natural log (Ln) 2 divided by the slope of lnPSA versus time. Descriptive statistics will be presented to summarize the PSA doubling time at baseline and after 12 weeks of protocol therapy as well as the change between time points. Pearson''s correlation will be used to estimate the relationship between pre-treatment PSA doubling time and percent change in PSA doubling time after 12 weeks of protocol therapy. In an exploratory fashion, the mean percent change in PSA doubling time after 12 weeks of protocol therapy from pre-treatment PSA doubling time will be calculated

for the subsets of patients with and without a decline in serum PSA on therapy. Either a dependent t statistic or the Wilcoxon matched pairs test will be performed for the subset of patients without a PSA decline to describe any change in PSA doubling time from pretreatment and for the full study cohort.

Safety and Pharmacokinetics:

All patients who receive at least one dose of study drug will be analyzed for safety. Safety endpoints including vital signs, adverse events, and clinical laboratory parameters will be summarized using descriptive statistics. All adverse events will be tabulated by grade according to CTCAE version 4.03, according to the worst grade experienced.

Descriptive statistics including the mean, standard deviation, and range of steady-state trough serum levels of itraconazole and its active metabolite hydroxy-itraconazole will be determined.

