The two most recent measurements of serum testosterone prior to Day 1 of protocol therapy must fulfill the following criteria:

- Both measurements are greater than 150 ng/dL.
- The two measurements are spaced at least 14 days apart.
- Both must be measured within 3 months of Day 1 of protocol therapy.
- There must not be an increase of > 50 ng/dL between these two successive measurements.
- 10. PSA doubling time (PSADT) ≤ 15 months, calculated based upon all serum PSA measurements obtained within 3 months prior to Day 1 of protocol therapy, witha minimum of three PSA measurements spaced at least 14 days apart (see section 6). PSA values obtained when serum testosterone was known to be less than 150 ng/dL, prior to local therapy, or within three months of last dose of LHRH agonist/antagonist or antiandrogen will be excluded from the calculation of the PSADT.PSADT calculation to be carried out using the following website:

http://nomograms.mskcc.org/Prostate/PsaDoublingTime.aspx

- 11. Total bilirubin less than 1.5 times upper limit of normal (ULN), or less than 3 times ULN at study entry in a patient with documented Gilbert"s disease.
- 12. ALT and AST levels less than 1.5 times ULN at study entry
- 13. Serum potassium greater than 3.5 mmol/L without oral supplementation
- 14. No history of uncontrolled hypertension (blood pressure > 160/100 mm Hg despite antihypertensive medication)
- 15. ECOG performance status of 0 or 1
- 16. Estimated life expectancy greater than 5 years
- 17. Age greater than or equal to 18 years at time of study entry
- 18. Ability to sign written informed consent

Phase II - Itraconazole

- 19. Ability to swallow study drug whole as a capsule
- 20. Primary prostate cancer tissue available for analysis is not required for inclusion onto this study but is strongly encouraged.
- 21. Patients who have partners of childbearing potential must be willing to use a method of birth control with adequate barrier protection as determined to be acceptable by the principal investigator and sponsor during the study and for 1 week after last study drug administration.

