5.3.2.1 PSA Kinetics

Mean Change From Baseline in PSADT

The mean change from baseline in PSADT after 12 weeks of protocol therapy will be measured for patients treated with itraconazole. A prior retrospective analysis of four non-hormonal agents tested in the biochemically relapsed setting identified change in the pre-treatment vs. on-treatment natural log PSA slope as an independent prognostic factor with respect to development of metastatic disease [37]. Novel agents tested in BCR may have clinical benefit without causing PSA decline but by slowing the rate of PSA rise instead, especially for agents with a cytostatic effect on tumor cells. It is not known if itraconazole has either cytocidal or cytostatic activity (or neither) in biochemically relapsed prostate cancer, and thus measuring both declines in PSA and changes in PSA kinetics is warranted.

Time to PSA Progression

The PCWG2 has suggested that duration of clinical activity is a key intermediate endpoint in initial phase II trials of agents conducted in the BCR disease population [36]. Indeed, in an exploratory analysis of a trial of IADT in BCR patients, Yu and colleagues demonstrated that in patients who completed the first cycle of IADT, a shorter duration of the first "off treatment" interval was associated with a shorter time to developing castrate resistant prostate cancer and shorter overall survival [41]. In the proposed trial, the median time to PSA progression on itraconazole therapy will be evaluated. The definition of PSA progression, as outlined in Section 2 (> 50% and >2 ng/mL above nadir (or above baseline if no PSA decline), is acknowledged to be arbitrary but does reflect PCWG2 guidelines for PSA progression in the castrate-resistant disease setting.

Given the heterogeneity of the study populations in prior studies of non-hormonal agents evaluated in BCR, as well as the variable definition of PSA progression used in prior clinical trials, using historical data to generate accurate estimates of median time to PSA progression is problematic. The analysis in the current study is exploratory in nature, aimed at generating preliminary estimates of the impact of itraconazole on the time to PSA progression.

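### The exploratory doubling-time test in men without a PSA decline selects on its own outcome, and its bias has no fixed sign, so its p-value cannot be read as a drug effect

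*Combined protocol and SAP*

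**What the plan says.** Section 10.8.2 derives doubling time, before and on treatment, as "natural log (Ln) 2 divided by the slope of lnPSA versus time". Baseline uses all PSA values from the 3 months before Day 1, with a "minimum of three PSA measurements spaced at least 14 days apart" (4.2, criterion 10). The same criterion admits only men whose doubling time from those values is 15 months or less. On treatment, PSA is monthly (6.3.5).

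The subset step is introduced as exploratory. Mean percent change is to be calculated "for the subsets of patients with and without a decline in serum PSA on therapy". Then a paired t or Wilcoxon test "will be performed for the subset of patients without a PSA decline to describe any change in PSA doubling time from pretreatment". The sentence does not stop there; its purpose reads in full "to describe any change in PSA doubling time from pretreatment and for the full study cohort". So the full cohort is tested as well.

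Section 10.8.2 does not say how large a decline must be, at which visit, against which reference value, or whether it needs confirmation. It also does not say whether the Day 1 PSA enters either slope. By contrast, the primary endpoint (10.7.1, 10.8.1) needs a confirmed fall of at least 50%. PSA progression (10.8.2) needs a rise above 50% and above 2 ng/mL, confirmed. Section 10.8.3 ends by stating that secondary and correlative analyses get no multiplicity adjustment.

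**The concern.** The flag that sorts men into the subset and the slope tested inside it come from the same few PSA values. A man whose week 4 PSA happens to read low, or whose Day 1 PSA happens to read high, is labelled a decliner and leaves. The errors of the men who stay are no longer centred on zero, so their average slope no longer estimates their true growth. Section 1.3.3 warns of this variability: it reports that 40% of placebo men in a cited trial had doubling time lengthen to more than 150% of baseline.

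Section 5.3.2.1 explains why kinetics are measured: "Novel agents tested in BCR may have clinical benefit without causing PSA decline but by slowing the rate of PSA rise instead". Men without a decline are where a reader would naturally look for that pattern. A significant result there, in either direction, could be reported at face value as slowing or as failure to slow.

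**Working it through.** **The plan's own figures.** None is given for the doubling-time test: no sample size, power, SD or effect. The only design figures are for the primary endpoint (10.2), and they reproduce: exact power 0.803, one-sided error 0.0398, probability of early stopping 0.620.

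**Assumptions not in the documents.** PSA grows log-linearly. Error SD on the log scale is 0.05, 0.10 or 0.15. True doubling time is lognormal with median 9 months and log-spread 0.5. There are three pre-treatment values (2.5, 1.5 and 0.5 months before Day 1), then Day 1 and weeks 4, 8 and 12. Each trial has 40 men and uses two-sided 5% paired t tests on the slope.

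**Step 1. How often does noise alone give a decline?** Growth in ln PSA over 4 weeks is g = ln 2 × (28/30.44) / doubling time in months. The chance that week 4 reads below Day 1 is Φ(−g / (√2 × SD)).
- Doubling time 6 months: g = 0.106. At SD 0.05, Φ(−0.106/0.0707) = Φ(−1.50) = 7%. At SD 0.15, Φ(−0.106/0.212) = Φ(−0.50) = 31%.
- Doubling time 15 months: g = 0.0425. The same steps give Φ(−0.60) = 27% and Φ(−0.20) = 42%.

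Over three visits, 19 to 48% of untreated men have at least one value below Day 1.

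**Step 2. Which way does the selection push the slope?** With visits at 0, 1, 2 and 3 (units of 4 weeks), the least-squares weights are −0.3, −0.1, 0.1 and 0.3. Dropping decliners drops men with high Day 1 errors. Day 1 has weight −0.3, so the remaining slopes are too steep. Without Day 1 the weights on weeks 4, 8 and 12 are −0.5, 0 and 0.5. Week 4 is where expected growth is smallest and noise most often causes a dip. Dropping low week 4 errors then leaves slopes that are too shallow.

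**Step 3. Size, any-visit rule, SD 0.05 to 0.15.**

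| Setting | Result in the no-decline subset | Full cohort |
|---|---|---|
| No entry rule, Day 1 in slope, no drug effect | slope overstated 3 to 31% | no selection |
| No entry rule, Day 1 in slope, growth halved | slope overstated 14 to 93% | no selection |
| No entry rule, Day 1 out, no drug effect | slope understated 5 to 19% | no selection |
| Entry at 15 months or less, Day 1 in, no drug effect | false slowing in 18 to 22% of trials; essentially no false acceleration | false slowing in 38 to 93% of trials |

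The nominal rate in each direction is 2.5%. The last row reflects regression to the mean: men enter partly because noise made their baseline slope steep.

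**Step 4. A second model.** Here true doubling time is uniform from 3 to 15 months, pre-treatment PSA is at weeks −12, −8 and −4, Day 1 enters both slopes unless stated, and there is no drug effect. Entries are the change in slope at SD 0.05 / 0.10 / 0.15.
- No entry rule, any visit: subset +6% / +30% / +74%; full cohort about 0%.
- Entry rule, any visit: subset −2% / +1% / +4%; full cohort −7% / −21% / −34%.
- Entry rule, week 12 below Day 1: subset −7% / −13% / −15%.
- Entry rule, any visit, Day 1 out of both slopes: subset −12% / −30% / −45%.

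With no drug effect in any row, the subset result runs from +74% to −45%, depending on the noise level, on whether the entry rule is modelled, and on choices that 10.8.2 leaves open. With the entry rule in place it still runs from +4% to −45%.

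**The case against.** The strongest reply is that little hangs on this test. It is labelled exploratory and descriptive, no decision rule uses it, and the full cohort is tested alongside it. All of that stands, and it limits the point to how one exploratory result may be read.

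A reader might go further and infer that the subset test is biased against slowing. Without the entry rule and with Day 1 in the slope, simulated power to show a halving of growth is 0.26 in the subset against 0.88 in all men (SD 0.10), and 0.04 against 0.59 (SD 0.15). The documents do not support that as a general statement. The trial does have an entry rule on baseline doubling time, and 10.8.2 does not put Day 1 in the slope. A Wilcoxon run on doubling time with the entry rule (SD 0.15, growth halved) detects slowing in 0.66 of subsets. Nor is the subset made of noise alone: true growth and any real drug effect also decide membership.

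A second tempting inference is that the full-cohort slope test is an unbiased replacement. It is not. Under the entry rule it shows false slowing more often than the subset test does (38 to 93% against 18 to 22%).

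One might also keep the test and simply define decline more strictly. With a fall of at least 25% at two consecutive visits, noise-only decliners drop to 0 to 0.7% in the second model. But under the entry rule the subset then shows the same spurious slowing as the full cohort (−8% / −21% / −33%). A definition cures the sorting problem but does not make the p-value a drug effect.

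**Conclusion.** The point holds in a limited form. The test conditions on its own outcome, noise moves a sizeable share of men between subsets, and the net sign of the bias is not fixed. It depends on whether Day 1 enters the slope, on what counts as a decline, and on how strongly entry selection acts. The subset p-value therefore cannot support a claim of slowing or a claim of no slowing.

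The mechanism can be read directly from 4.2 and 10.8.2. The sizes rest on assumed PSA noise and an assumed spread of doubling times, neither of which the documents give. The primary endpoint is not affected.

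**What to change.** In 10.8.2:
- Delete the significance test in the subset without a PSA decline.
- Show both subsets descriptively, give the rule used for decline, and state that the subsets are defined by the on-treatment PSA that also determines the slope.
- Keep the full-cohort paired comparison, but on the ln PSA slope scale (on-treatment minus pre-treatment). Doubling time is ln 2 over the slope and becomes unstable when the slope is near zero or negative.
- State whether the Day 1 PSA enters each slope.
- State that selection on baseline doubling time makes even the full-cohort change lean toward slowing, so it is not a clean estimate of drug effect.

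The cost is a few sentences of wording and no new data. The downside is the loss of one exploratory p-value.

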10.8.3 Analytic Plan for the Correlative Objectives

Endocrine Parameters

Serum hormone levels, including testosterone, androstenedione, DHEA-S, cortisol, aldosterone, 11-deoxycortisol, ACTH, and deoxycorticosterone, will be measured at baseline, at week 4, week 12, and at the time of PSA or clinical progression. To summarize the outcome, descriptive statistics including the mean percent change from baseline in serum hormone levels at 4 and 12 weeks will be presented with a standard deviation and Pearson"s correlation will be used to estimate the relationship between the baseline hormone level and percent change in hormone level after 4 and 12 weeks of treatment. Analysis of variance (ANOVA) methods for mixed models allowing for variable number of follow-up measurements with linear contrasts will be used to evaluate the change in serum hormone levels after 4 and 12 weeks of protocol therapy. It is hypothesized that approximately 15% of patients treated with protocol therapy will achieve a PSA decline \geq 50%. Depending upon the observed frequency, the ANOVA model will include a factor to test for the effect of PSA decline on change in serum hormone levels. Otherwise, analyses will compare the baseline and percent change in serum hormone levels at 4 and 12 weeks between patients achieving a PSA decline $\geq 50\%$ or not using a two group t statistic. For these exploratory analyses, graphic presentations will also be used to explore the overall pattern of change in serum hormone levels between those with and without a PSA decline.

Hedgehog Pathway

The quantitative expression of *GLI1*, a downstream product of the Hedgehog signal transduction pathway, will be measured by quantitative RT-PCR from serial skin biopsies obtained at baseline and after 4 weeks of therapy. The fold change in expression level after 4 weeks of protocol therapy will be calculated for each patient. Descriptive statistics will be used to summarize the proportion of patients with down-regulation of *GLI1* expression after 4 weeks of treatment with itraconazole. Down-regulation will be defined as any magnitude of decrease in *GLI1* mRNA expression after 4 weeks of protocol therapy compared to baseline expression level. The patient

cohort will be dichotomized by whether there is up- or down-regulation of *GL11* expression. Fisher's exact test will be used to test for an association between down-regulation of *GL11* expression and PSA decline 50% on protocol therapy. The probability distributions for each *GL11* expressionsubset (as defined above) of the time to PSA progression will be estimated using the Kaplan-Meier product limit method. The results will be summarized by the estimated median with 95% confidence intervals. An exploratory analysis using the log-rank test will be used to test for differences in the distributions between patients with down-regulation of *GL11* expression vs. those without *GL11* down-regulation on therapy.

The quantitative expression of *GLI1* will also be measured by quantitative RT-PCR from archived primary prostate cancer tissue. The patient cohort will be dichotomized by expression level of *GLI1* (above vs. below the median). Fisher's exact test will be used to test for an association between *GLI1* expression in primary prostate cancer tissue and PSA decline $\geq 50\%$ on itraconazole therapy. The probability distributions for each *GLI1* expression subset of the time to PSA progression will be estimated using the Kaplan-Meier product limit method. The results will be summarized by the estimated median with 95% confidence intervals. An exploratory analysis using the log-rank test will be performed to test for differences in the distributions between patients with *GLI1* expression above vs. below the median from primary prostate cancer tissue specimens.

Immunohistochemical analysis of primary prostate cancer tissue for protein expression of *PCTH1*, *GL11*, *SMO*, as well as Sonic hedgehog ligand will be carried out for patients with evaluable tissue. It is estimated that approximately 50% of patients will have tissue available for analysis. Immunohistochemical expression will be graded as 0, 1+, 2+, and 3+ staining intensity by independent, blinded pathologic assessment. For each protein, the patient cohort will be dichotomized based on intensity of IHC staining (0 and 1+ vs. 2+-3+). Fisher''s exact test will be used to test for an association between IHC expression and PSA decline > 50% on protocol therapy. The probability distibutions for each expression subset of the time to PSA progression will be estimated using the Kaplan-Meier product limit method. The results will be summarized by the estimated median with 95% confidence intervals.

No adjustment for multiple comparisons will be made for the analysis of the secondary and correlative objectives.

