2.0 Hypothesis and Study Objectives

2.1 Hypothesis

A significantly greater proportion of patients treated withitraconazole will achieve at least a 50% decline from baseline in serum PSA after 12 weeks of therapy, as compared to a historical control based upon the PSA response proportion observed in prior phase II clinical trials of other non-castrating therapiesin men with biochemically relapsed hormone sensitive prostate cancer. Favorable results with respect to PSA modulation, along with parallel findings demonstrating acceptable toxicity, potent Hedgehog pathway inhibition, and absence of significant impact on serum hormone levels, would form the basis for the further study of itraconazoleas a potentially viable non-castrating treatment option for men with biochemically relapsed prostate cancer.

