5.3.3 Correlative Endpoints

5.3.3.1 Endocrine Parameters

The mean change from baseline in serum androgen levels, including testosterone, DHEA-S, and androstenedione after 12 weeks of therapy with itraconazole will be determined to investigate further the mechanism of action of itraconazole in prostate cancer. Prior study in CRPC provided preliminary evidence that itraconazole, unlike the related azole compound ketoconazole, has a mechanism of action distinct from androgen synthesis inhibition [19], albeit in a castrate patient population. Demonstrating in the current study, with a non-castrate patient population, that itraconazoletherapy concurrently does not significantly impact serum androgen levels yet modulates serum PSA will lend further support to the hypothesis that itraconazole has a mechanism of action distinct from ketoconazoleand androgen synthesis inhibition. The main limitations of this particular analysis is that serum hormone levels may not reflect intra-tumoral androgen concentrations, and that this patient population is non-castrate with a different systemic hormonal milieu than the previous study in CRPC.

In the prior clinical trial of itraconazole in CRPC, there were several patients with a constellation of adverse events including hypokalemia, hypertension, and peripheral edema [19]. This constellation of symptoms has also occasionally been observed in prior studies of high dose itraconazole in patients with chronic fungal infections, and raises the possibility of induced mineralocorticoid excess. Serum aldosterone levels were measured in the prior study of itraconazole in CRPC (and were not elevated on therapy); however upstream compounds within

the adrenal synthetic pathway with mineralocorticoid activity, including deoxycorticosterone (DOC) and 11-deoxycortisol were not measured. A more comprehensive panel of adrenal and pituitary hormones, including ACTH, DOC, aldosterone, and 11-deoxycortisol, will be measured on a serial basis in the current study and the mean change from baseline will be determined.

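### The reported hormone endpoint, an arithmetic mean of percent change, sits above zero when the drug has no effect and understates a modest androgen fall; a log-ratio endpoint avoids this

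*Combined protocol and SAP*

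**What the plan says.** The endpoint list in Section 10.7.3, repeating Section 3.2.3, reads "Mean percent change from baseline in serum androgen levels, including serum testosterone, DHEA-S, and androstenedione, after 4 and 12 weeks of protocol therapy". A parallel item covers ACTH, aldosterone, DOC, 11-deoxycortisol and cortisol. Section 10.8.3 reports the endpoint descriptively, with a standard deviation: "descriptive statistics including the mean percent change from baseline in serum hormone levels at 4 and 12 weeks will be presented". No log scale, geometric mean or median is named for hormones.

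The same paragraph gives a separate method for inference: "Analysis of variance (ANOVA) methods for mixed models allowing for variable number of follow-up measurements with linear contrasts will be used", in order to "evaluate the change in serum hormone levels after 4 and 12 weeks of protocol therapy". The scale of that model is not stated. Percent change enters two further analyses: a Pearson correlation with the baseline level, and a two-group t comparison by PSA response that serves as a fallback ("Otherwise, analyses will compare the baseline and percent change in serum hormone levels at 4 and 12 weeks between patients"). The paragraph calls the work exploratory: "For these exploratory analyses, graphic presentations will also be used to explore the overall pattern of change in serum hormone levels".

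The result has a purpose. Section 2.1 counts "absence of significant impact on serum hormone levels" among the findings that would support further study. Section 5.3.3.1 says that showing itraconazole "does not significantly impact serum androgen levels yet modulates serum PSA will lend further support to the hypothesis" of a mechanism other than androgen synthesis inhibition. No margin for an unimportant change is set.

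**The concern.** Percent change cannot go below -100% but has no upper limit. When baseline and follow-up both vary at random, a man whose baseline happens to be low contributes a large positive value, and a man whose baseline happens to be high contributes a smaller negative one. The average is therefore pulled upward without any drug effect.

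For testosterone, DHEA-S and androstenedione the hoped-for finding is no fall, and an upward pull makes a modest fall look smaller or absent. With no margin set, readers are likely to judge androgen effect from the reported mean. Some within-man variation is to be expected: the schedule footnote asks for morning sampling only where possible, and the table in Section 9.1 allows testosterone and DHEA-S at any time of day.

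**Working it through.** **Plan's own figure.** There is none to reproduce. The documents give no standard deviation, CV, power or margin for the hormone endpoint. The one sample size, 40 evaluable patients, is set on PSA response (Section 10.2).

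**Inputs.** From the documents: the endpoint definition (Sections 3.2.3, 10.7.3, 10.8.3), n = 40 (Section 10.2), and the ketoconazole falls of 54, 90 and 58% for DHEA, DHEA-S and androstenedione (Section 1.2.1). Assumed: within-man CV 20 to 50%; error independent and lognormal at the two visits; for the power check, between-man CV 40% and a two-sided 5% test. The 15% fall is an illustration, not a threshold in the protocol.

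**Step 1, expected value.** Let X be baseline, Y follow-up, f the true proportional fall, and s² = ln(1 + CV²) the log-scale error variance at each visit. Then ln(Y/X) is normal with mean ln(1 - f) and variance 2s², so

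E[Y/X] - 1 = (1 - f) × exp(s²) - 1 = (1 - f)(1 + CV²) - 1.

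With f = 0 this is CV². The fall that is exactly cancelled is 1 - 1/(1 + CV²).

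**Step 2, numbers.** For example, at CV 30% a 15% fall gives 0.85 × 1.09 - 1 = -7.35%.

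| Assumed CV | No effect reads as | 15% fall reads as | Fall cancelled | 54% fall reads as | 90% fall reads as |
|---|---|---|---|---|---|
| 20% | +4% | -11.6% | 3.8% | -52.2% | -89.6% |
| 30% | +9% | -7.35% | 8.3% | -49.9% | -89.1% |
| 40% | +16% | -1.4% | 13.8% | -46.6% | -88.4% |
| 50% | +25% | +6.25% | 20.0% | -42.5% | -87.5% |

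The mean log ratio has expectation ln(1 - f), so it is centred on zero under no effect. In simulation with n = 40, its back-transformed geometric mean was within about 0.6 percentage points of zero at every CV in the table.

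**Step 3, the planned inference.** A paired t test on raw levels is a simple stand-in for a mixed model on levels. It was compared with a t test on log ratios (n = 40, 20,000 simulated trials). With no effect, each rejects in about 2.5% of trials on either side, so neither carries the bias. Power for a true 15% fall:

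| Assumed CV | Raw levels | Log ratio | Gain |
|---|---|---|---|
| 25% | 75.1% | 82.0% | 6.9 points |
| 30% | 60.4% | 67.5% | 7.1 points |

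**The case against.** The strongest reply is that the percent change is a descriptive summary, while the analysis that evaluates hormone change is the mixed model on levels. This stands. A reader might infer that the plan's test would miss a real androgen fall or falsely declare a rise. The documents do not support that: Section 10.8.3 contains no one-sample test of percent change, and its model is worded in terms of levels.

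The second reply is that the mechanistic contrast is with ketoconazole, and falls of that size stay plain on either scale. This also stands; the exposure is to modest falls only.

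Three further inferences go too far.

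- The bias does not favour the sponsor for every hormone. Section 5.3.3.1 raises possible mineralocorticoid excess, so for DOC and 11-deoxycortisol a rise is the worry, and an upward pull works against a reassuring result.
- The bias does vary with each hormone's variability, but no comparison across hormones is planned, so nothing in the plan is spoiled by that.
- In the fallback comparison by PSA response, the bias is present in both groups and largely cancels if their variability is similar.

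Finally, the size rests on CVs that the documents do not give. For testosterone, the entry floor of 150 ng/dL could produce some regression to the mean in the opposite direction if the screening sample also serves as baseline.

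What the reply does not remove is that the biased mean is the defined endpoint, and that the scale of the model is left open.

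**Conclusion.** The point holds for the reported endpoint and not for the planned inference. Given independent lognormal error, the mean percent change is too high by CV² under no effect: +4 to +25% over an assumed CV of 20 to 50%. A true 15% fall would be reported as anything from about -12% to +6%. For the androgens this favours the conclusion of no effect, while falls of 54 to 90% would remain evident. A mixed model on raw or log levels is free of the bias, and choosing logs gains about 7 points of power for a 15% fall at CV 25 to 30%. The matter is minor: the endpoint is correlative and exploratory, and the PSA primary analysis and the stopping rules are untouched.

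**What to change.** In Sections 3.2.3, 10.7.3 and 10.8.3, and in the matching objectives in Section 2.2.3:

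1. Define the hormone endpoint as the log ratio of the week 4 or week 12 value to baseline.
2. Report it as the geometric mean percent change with a 95% confidence interval.
3. State that the mixed model is fitted to log hormone levels.
4. Use log ratios in the fallback comparison by PSA response and in the correlation with baseline.
5. Keep the arithmetic mean percent change as description only.

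The cost is wording. No new samples, visits or patients are needed. The log scale is already in use in Section 10.8.2, where PSA doubling time is taken from the slope of log PSA. One added line should say how values below an assay's limit are handled, because they have no usable logarithm.
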